H_{1a} will be tested by the significance of the [group x time] contrast from Baseline to POST-4wk for the 6-minute walk test at $\alpha=0.05$. For H_{1b}, secondary outcomes will be tested separately using the same model as H_{1a} to identify the most sensitive measures to carry forward into future studies.¹¹⁰ The Benjamini-Hochberg procedure²²³ will be used to control the false discovery rate (FDR) for the secondary outcomes.

Aim 2: Determine the minimum locomotor training duration needed to maximize immediate effects

Hypothesis 2a (H_{2a}): Within the HIT group, *walking capacity* (6 minute walk test distance) and *secondary outcomes* will significantly increase from 4WK to 8WK and from 8WK to 12WK

Hypothesis 2b (H_{2b}): Compared to MAT, HIT will elicit significantly greater improvements in *walking capacity* and *secondary outcomes* from PRE to 8WK and from PRE to 12WK

H_{2a} will be tested by the significance of the respective time contrasts within the HIT group. **H_{2b}** will be tested by the significance of the respective [group x time] contrasts. Secondary outcomes will have FDR control.²²³

Data and Safety Monitoring Plan

An adverse event (AE) is an undesired medical occurrence in a participant who is undergoing study procedures and does not necessarily have a causal relationship with the treatment or study procedures. This includes any adverse clinical change that occurs at any time following consent. A serious AE (SAE) is any adverse experience occurring during study participation that results in any of the following outcomes: death; a life threatening situation; inpatient hospitalization or prolongation of existing hospitalization; a persistent or significant disability/incapacity.^{209,210} The data and safety monitoring plan for this study will include participant monitoring for AEs and other problems, review of AEs and other problems by the study team and IRB, and an independent data safety monitoring board (DSMB).

Participant safety monitoring

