Risk of any breach to participant privacy or confidentiality will be minimized by: 1) maintaining all physical participant files in locked filing cabinets; 2) minimizing use of participant identifiers on data collection forms, electronic files and the secure REDCap web-database; 3) not storing any participant identifiers on peripheral devices used for data processing (e.g. electronic walkway for gait testing, iPod application used for heart rate data); 4) only allowing de-identified data exports from REDCap and ensuring that the final dataset does not include any identifiers or other variables that could lead to deductive disclosure of individual participant identities before submitting it to a public research data archive (e.g. NIH/NICHD data and specimen hub [DASH]); 5) uploading files that need centralized review (e.g. clinical brain imaging data and metabolic cart data files from exercise testing) to a secure server designed for research data (REDCap or a UC research data server); 6) only allowing study personnel and laboratory staff (e.g. Cardiac Stress Laboratory) to access the data and giving only as much access as necessary to perform study roles and ensure participant safety; and 7) destroying the link between participant identifiers and participant ID number after the final data analysis is completed.

E.4. Setting

Most study activities will be performed in rehabilitation/exercise research laboratories at each site. Stress testing will be conducted in either clinical or appropriately equipped research exercise testing laboratories.

E.5. Laboratory Methods and Facilities

None

E.6. Estimated Period of Time to Complete the Study

We estimate that each participant will be involved in the study for approximately 5 months and that the overall study will take approximately 5 years to complete.

F. HUMAN SUBJECTS

F.1. Sample Size

Approximately 17 participants (up to 30) will be enrolled in this study at each site (UC, UD, KUMC). Approximately 50 total participants (up to 75) will be enrolled in the study.

F.2. Eligibility Criteria

Table 3. Eligibility Criteria

Inclusion Criteria	Exclusion Criteria

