Hypothesis 2: To test the hypothesis that, compared with 4 and 8 weeks of HIT, 12 weeks of HIT will elicit significantly greater improvements in walking capacity and increased benefit over MAT, the same general linear model described above will be used. The hypothesis that 12 weeks of HIT will elicit greater improvements in primary and secondary outcomes compared to 4 and 8 weeks of HIT will be tested by the significance of the respective time contrasts within the HIT group. The hypothesis that HIT will elicit significantly greater improvements in primary and secondary outcomes from PRE to 8-WK and PRE to POST compared to MAT will be tested by the significance of the respective [group x time] contrasts. False discovery rate control will be applied for secondary outcomes.³

Prognostic Factor Testing

We will also test for baseline cofactors that may influence a stroke survivor's response to the interventions in this study. To do this, we will utilize a multivariate prognostic model that includes comfortable gait speed, lower extremity Fugl-Meyer motor scores, and scores on the Activities-Specific Balance Confidence Scale. These measures were selected based on previous studies suggesting that comfortable gait speed,⁴⁻⁹ lower limb Fugl-Meyer motor scores,⁹⁻¹¹ and balance abilities¹² may influence response to gait rehabilitation interventions in individuals with chronic stroke. Other potential cofactors will also be explored to inform future studies.

Safety Data Analysis

We expect a similar rate of non-serious adverse events (AEs) between HIT and MAT (e.g. temporary exercise-related soreness and fatigue), without any study-related serious AEs. In the unexpected event of one or more serious adverse events (SAE), the SAE rate will be compared between groups to confirm that there is no significant difference in major safety risk between HIT and MAT. A logistic regression model will be used for this analysis with SAE (yes/no) as the dependent variable and fixed effects for group, site, and baseline gait speed category. If there are SAE(s) in one group only, a continuity correction (0.5 SAEs added to each group) will still allow the odds ratio to be calculated.¹³

References

2. Dobkin BH. Progressive Staging of Pilot Studies to Improve Phase III Trials for Motor Interventions. *Neurorehabil Neural Repair*. 2009;23(3):197-206.

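### At low SAE counts the adjusted logistic model has no full maximum likelihood fit, and the 0.5 correction is not defined across site and gait-speed cells (minor)

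*SAP*

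**What the plan says.** The SAP, under Safety Data Analysis, sets the trigger: "In the unexpected event of one or more serious adverse events (SAE), the SAE rate will be compared between groups". The model has "SAE (yes/no) as the dependent variable and fixed effects for group, site, and baseline gait speed category". If SAEs occur in one arm only, "a continuity correction (0.5 SAEs added to each group) will still allow the odds ratio to be calculated". The protocol's Safety Data Analysis paragraph in E.2 gives the same trigger, model and correction. Both cite the pilot trial for the correction, and its worked use is in protocol Table 7.

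Three further statements set the likely event count:
- The SAP expects the trial to run "without any study-related serious AEs".
- The protocol's definition of an adverse event is all-cause: "This includes any adverse clinical change that occurs at any time following consent". An SAE includes any inpatient hospitalisation.
- On size, "Approximately 50 total participants (up to 75) will be enrolled in the study", at three sites with about 17 each.

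Neither document says which site and speed cell receives a half-event, how half an event enters a participant-level yes/no outcome, or what happens when a site or speed category has no SAE. No sparse-data method is named as a fallback.

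**The concern.** The model has five parameters: an intercept, one for group, two for site and one for speed category. It is called on at counts as low as one. A site without an SAE sends its coefficient to minus infinity, so the fit as specified does not converge to a finite solution. The stated repair deals with an empty arm, not with an empty site or speed category. Because it is stated per arm, the analyst must decide, after the events are known, where in the six site-by-speed strata the half-events go.

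At stake is the reproducibility of the leading safety contrast; the protocol labels the AE grade and category analyses as secondary. Two analysts following the text could report different odds ratios from the same data.

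**Working it through.** **Inputs.** From the documents: 50 participants, three sites of about 17, two speed categories, two equal arms, and the terms and trigger above. Assumed, because the documents do not say: 30% of participants below 0.4 m/s (15% to 50% also tried), near-balanced cells, SAEs falling at random, and half-events added with denominators unchanged, as in Table 7.

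**1. The plan's own precedent.** Table 7 reproduces from arm totals alone, with sessions as denominators (141 HIT, 60 MAT):

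OR = [(a + 0.5)/(141 − a − 0.5)] / [0.5/(60 − 0.5)]

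- Related fatigue, 3 v 0: (3.5/137.5)/(0.5/59.5) = 3.03; printed 3.03.
- 2 v 0: (2.5/138.5)/(0.5/59.5) = 2.15; printed 2.15.
- 1 v 0: (1.5/139.5)/(0.5/59.5) = 1.28; printed 1.28.

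No site or speed term is involved. The precedent therefore shows how the correction works for two groups, but not how it enters the adjusted model.

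**2. When the full fit exists.** With one or two SAEs and three sites, at least one site has none, so failure is certain. For higher counts, simulated datasets were checked for separation by linear programming:

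| SAEs | No finite full fit |
|---|---|
| 1 or 2 | 100% |
| 3 | about 90% |
| 4 | about 67% |
| 5 | about 47% |
| 8 | about 12% |

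Over 15% to 50% slow walkers, the share without a full fit is 87% to 93% at three SAEs and 42% to 64% at five. With 75 participants the pattern is similar.

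**3. What happens to the group term.** In the simulations the group coefficient was non-finite only when all SAEs were in one arm: 100% of datasets at one SAE, 49% at two, 24% at three, 11% at four and 5% at five. With SAEs in both arms it stayed finite even when a site or speed term diverged. For example, one SAE per arm at the same site gives a group OR of 1.00.

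**4. Where the half-events go.** The unadjusted corrected OR for one HIT SAE, 25 per arm, is (1.5/23.5)/(0.5/24.5) = 3.13. In the adjusted model there are 6 HIT cells × 6 MAT cells = 36 single-cell placements. One of them can be checked by hand. If both half-events go into the stratum that holds the SAE, every other stratum is empty and the group OR reduces to that stratum's own table, with h HIT and m MAT participants:

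OR = [1.5/(h − 1.5)] / [0.5/(m − 0.5)]

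- h = 3, m = 2: 1.00/0.333 = 3.0
- h = 3, m = 3: 1.00/0.20 = 5.0
- h = 2, m = 2: 3.00/0.333 = 9.0
- h = 2, m = 3: 3.00/0.20 = 15.0

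Slow cells of two or three per arm are what 17 × 0.30 ≈ 5 slow walkers per site gives. Over all 36 placements the OR ran from roughly 2.8 to 4.7 in most layouts; individual layouts with larger cells go a little outside this, from about 2.3 to 5.6. Only where the event cell held two HIT participants did it reach 9 to 15. With three HIT and two MAT slow walkers at the affected site, 30 of the 36 placements still left a site or speed term divergent.

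For two SAEs in one arm at different sites the range was 5.3 to 6.2 (unadjusted 5.44). For three it was 7.8 to 9.7 (unadjusted 7.98).

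**5. Against the uncertainty.** For 1 v 0 the corrected 95% intervals ran from about 0.1 to between 80 and 150. Every corrected interval computed included 1.

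**6. An alternative on the same terms.** Firth logistic regression with no half-events gave finite estimates for every term. The group ORs, with Wald intervals, were 2.74 (0.21 to 35.7) for 1 v 0, 5.01 (0.37 to 68) for 2 v 0 and 6.86 (0.51 to 93) for 3 v 0.

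**The case against.** The best defence is that the planned quantity is the group odds ratio, not the site or speed coefficients. That ratio was infinite only when one arm had no SAE, which is exactly when the correction applies. Divergent nuisance terms are untidy but do not spoil the safety contrast. This stands, and it disposes of one tempting inference: that datasets separated with SAEs in both arms leave the safety comparison without an answer. They do not.

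Three other readings go further than the documents allow:
- **That the model cannot be fitted whenever it is triggered.** The trigger has no upper limit and SAEs are all-cause. At eight SAEs about 88% of datasets have a full fit.
- **That the correction can never repair the site and speed terms.** Spreading the half-events over all strata makes every term finite. The plan does not say to do this, but it does not rule it out.
- **That a range of about 3 to 15, or an infinite ratio, is typical.** The value 15.0 comes from one of 36 placements, with 1.5 events among two people; the next highest is just under 7. Divergence with two SAEs required every occupant of a two-person cell to have had one. Even then only 3 of 30 feasible placements diverged, and spreading the half-events gave a finite 11.9.

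It is also fair to say that safety oversight does not rest on this model alone: a DSMB reviews the data and AE rates per session are analysed too. What remains is that the plan gives no placement rule and no fallback at the low counts it itself regards as the likely ones.

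**Conclusion.** The point holds as a specification gap. The absence of a full maximum likelihood fit is certain at one or two SAEs, usual at three or four, about even at five and uncommon by eight. These shares above two SAEs depend on the assumed 30% slow walkers, balanced cells and random SAEs. When SAEs are in one arm only, the reported adjusted odds ratio depends on an unstated placement of half-events. The effect is modest in most layouts and large only in a two-participant cell.

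A reader might infer that the trial's safety conclusion is at risk. The calculations do not support that: placement effects are small beside the intervals, and no conclusion was shown to change. The primary 6-minute walk analysis is not involved. Severity: minor.

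**What to change.** In the Safety Data Analysis sections of both the SAP and the protocol, replace the maximum likelihood fit and the 0.5 correction with Firth penalised-likelihood logistic regression on the same terms (group, site, gait-speed category), with profile penalised-likelihood confidence intervals. Beside it, report SAE counts by arm and an unadjusted risk difference with an exact confidence interval.

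The cost is about one sentence in each document and one option in PROC LOGISTIC in SAS, the software the SAP already names. The downside is slight shrinkage of the odds ratio towards 1 when events are few. An exact or group-only comparison stated in advance would also close the gap; Firth is suggested because it keeps the planned adjustment and needs no half-events to be placed.
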